The total required sample size for this study is **458 patients**. Assumptions for the power analysis include non-inferiority for VAP recurrence and superiority for antibiotic-free days in the intervention group, 3 planned analyses of the data with O'Brien-Fleming spending function with binding futility boundaries, 25% recurrence rate in the control group (14), and 6 enrolling centers with an average cluster size of 10. To detect a 10% difference in outcomes between groups with 80% power and assuming a 10% dropout rate, a total sample size of 458 patients is required for this study. Sample size will be recalculated at each interim analysis with better estimates based on accrued patients. The planned analyses will take place after enrollment of 150, 300, and all patients.

VII. Study-Wide Recruitment Methods

This is a multicenter randomized controlled trial. We have partnered with the Surgical Infection Society to aid in recruitment of interested centers for participation in the study. The recruitment methods for individual subjects to participate in the study will be uniform across all centers. A member of the research team at each center will screen all patients in their respective surgical ICUs by reviewing the medical record of each patient in the ICU for eligibility based on the inclusion and exclusion criteria listed in *Section V* (above). Screening will occur daily during the study period. We will be requesting a waiver of the requirement for written authorization

UM IRB No.: 20211211

NCT05545735

Protocol Date: November 14, 2023

Principal Investigator: [name]., M.S.P.H.

Study Title: The Duration of Antibiotic Therapy for Early VAP (DATE) Trial

from patients to access their health records due to the nature of the study. Please see further documentation in *Section XXXII* (below).

VIII. Study Timeline

Each individual patient enrolled in the study will be followed for 30 days or until hospital discharge, whichever occurs first. We will also review patient charts at hospital discharge to determine overall hospital length of stay and overall mortality, in addition to 30-day outcomes. We expect all subjects to be enrolled within the first 2 years of study across all centers, with full data analysis completed at 3 months after study completion.

IX. Study Endpoints

A) Primary Outcomes

- a.** VAP recurrence within 30 days
 - i.** VAP recurrence = VAP occurring 2 – 14 days following completion of initial therapy

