will be captured as clinical outcomes and do not need to be reported as SAEs unless felt related to study procedures.

XI. Data and Specimen Banking

There will be no specimen banking for this study.

XII. Data Management

All data will be collected on the attached case report form (CRF) and then input by study personnel at each individual site into the University of Miami REDCap electronic data management system. Each site PI will be responsible for keeping a secure file linking the patient medical record number (MRN) to their study ID in the event that additional information is required for study analysis, which will be destroyed at the conclusion of the study. All data will be entered into REDCap in a de-identified manner, using only the study ID, without including any personal identifying information. Data analysis will be performed by [name], PhD. [name] is a tenured Professor of Surgery and Public Health at the University of Colorado Denver and the Colorado School of Public Health, where she is also the Associate Director of the NIH-funded T32 postdoctoral research fellowship in trauma surgery, and statistical consultant to the Ernest E. Moore Shock Trauma Center at Denver Health Medical Center. Additionally, she is the former Statistical Editor for the *Journal of Trauma and Acute Care Surgery*, with over 30 years' experience in injury-related research, particularly in critically ill and injured patients.

Three equally spaced analyses (two interim and one final) will be conducted for all outcomes, using the O'Brien-Fleming alpha spending function. Data analyses will be performed using SAS v9.4 (SAS Inc., Cary, NC). Randomization will occur at the hospital level in blocks of 20. Data will be analyzed using an intention-to-treat strategy (i.e., data of patients randomized to receive 4 days of antibiotic therapy will be analyzed as belonging to this group even if they receive longer courses) and a per-protocol strategy (i.e., crossovers and protocol violations

UM IRB No.: 20211211

NCT05545735

Protocol Date: November 14, 2023

Principal Investigator: [name]., M.S.P.H.

Study Title: The Duration of Antibiotic Therapy for Early VAP (DATE) Trial

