excluded). Data will be expressed as median (interquartile range) or frequency (%). Normality of continuous variables will be assessed by visual inspection of histograms. Differences in the means of continuous normally distributed variables will be assessed using Student's t-test or ANOVA. Differences in the medians of non-normally distributed continuous variables will be assessed using the Wilcoxon rank sum or Kruskal-Wallis tests. Proportions will be compared using the chi-squared or Fischer's exact test, as appropriate. Univariate analysis of categorical outcomes will be expressed as the relative risk with 95% confidence intervals, with standard errors adjusted for intra-center clustering. A generalized estimating equation or linear mixed model (with appropriate transformation of outcome variables to approximate normality, if needed) will be fit to address possible confounding if randomization fails to assure equitable distribution. Baseline variables associated with randomization status at the $p < 0.25$ level by univariate analysis will be added to the model using a stepwise selection method. The overall contribution of the fitted model to predicting variability in the outcome of interest will be assessed using the likelihood ratio chi-squared test. The alpha error level is defined at 0.05, with statistical significance at $p < 0.05$. No adjustment for multiplicity of outcomes will be done as this is an exploratory (rather than confirmatory) trial, and all hypotheses are pre-planned. Adjustment for multiple comparisons in pre-planned hypotheses leads to more type II errors (19, 20).

XIII. Provisions to Monitor the Data to Ensure the Safety of Subjects

As mentioned previously (see *Section X*), a DSMB will be convened. The DSMB will meet after each planned interim analysis, review data collected across all sites, and submit a written report to the overall study PI, who will submit the report to the IRB. Data analysis will be performed by [name], as mentioned above (see *Section XII*).

Data will be monitored daily at each site and any adverse events will be reported to the site PI per local IRB regulations. Efficacy and safety data will be collected on CRFs and inputted into REDCap by study personnel at each site. The study will be terminated early if there are

UM IRB No.: 20211211

NCT05545735

Protocol Date: November 14, 2023

Principal Investigator: [name]., M.S.P.H.

Study Title: The Duration of Antibiotic Therapy for Early VAP (DATE) Trial

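### Under intention-to-treat, adjustment covariates are chosen by chance imbalance between arms and no lead result is named; a fixed covariate list is a cheap improvement

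*Combined protocol and SAP*

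**What the plan says.** Section XII always provides unadjusted results. "Proportions will be compared using the chi-squared" or an exact test, and "Univariate analysis of categorical outcomes will be expressed as the relative risk with 95% confidence intervals, with standard errors adjusted for intra-center clustering".

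An adjusted model (a generalized estimating equation or a linear mixed model) is conditional: it "will be fit to address possible confounding if randomization fails to assure equitable distribution". No criterion for that failure is given. The next sentence sets the candidates: "Baseline variables associated with randomization status at the $p < 0.25$ level by univariate analysis will be added to the model", by a stepwise method with no entry or stay level. The screen tests association with arm, not with outcome, and no covariate is named.

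The same section plans intention-to-treat and per-protocol analyses and does not limit the adjustment rule to either. It states: "Three equally spaced analyses (two interim and one final) will be conducted for all outcomes". Section VI gives the timing: "The planned analyses will take place after enrollment of 150, 300, and all patients". Nothing fixes the adjusted model across these looks.

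Section XIII lets the DSMB end the trial for clear benefit without saying which result is judged. The DSMB Charter is an attachment that was not available here.

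**The concern.** In an intention-to-treat comparison, a baseline difference between arms is the play of chance. A screen on that difference selects variables by luck, not by how well they predict recurrence. Adjustment gains precision from predictors of outcome, and those are usually discarded here. Because the screen is rerun on accruing data, the adjusted model can also change between looks. And since the text does not rank the two results, the choice can be left until both have been seen. At stake are some avoidable loss of non-inferiority power and an open choice of lead result.

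**Working it through.** **Inputs from Section VI.** 458 patients, "25% recurrence rate in the control group", and "To detect a 10% difference in outcomes between groups with 80% power and assuming a 10% dropout rate". Evaluable: 458 × 0.9 = 412, or 206 per arm. Looks at 150 and 300 become 135 and 270 evaluable.

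**Assumptions.** 10% read as a 10-point margin; 95% confidence interval; 1:1 allocation; one prognostic variable among 5 or 15 independent candidates; odds ratio 1.5, 2.0 or 2.7 per SD; stepwise entry/stay 0.05 or 0.15. The comparator is a fixed list of three variables, one of them prognostic.

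**The plan's own figure.** With 25% in both arms and a 10-point margin, n per arm = (z₁₋α + 0.8416)² × 2 × 0.25 × 0.75 / 0.10². One-sided 0.05 gives 232 per arm, 464 in total, and 516 after dropout (464/0.9). One-sided 0.025 gives 590, then 656. Neither is 458. Sidedness, intracluster correlation and boundary inflation are not stated, so this does not show 458 to be wrong, and the present point does not depend on it.

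**Step 1: omission.** Under randomization a baseline p-value is about uniform, so P(fails p < 0.25) = 0.75. Stepwise selection sees only what passed. In simulation (6,000 trials per setting, 412 patients, blocks of 20) the prognostic variable was adjusted for in 23–26% of trials when the model was always fitted. A second simulation, with 3 prognostic variables among 10, left each out in 74–78%.

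**Step 2: a possible separate trigger.** If the model were fitted only when some candidate has p < 0.05 between arms, the inclusion rate would be 0.05 + 0.20 × (1 − 0.95⁴) = 8.7% with 5 candidates and 0.05 + 0.20 × (1 − 0.95¹⁴) = 15.2% with 15. That trigger is assumed, so these figures are illustrative only.

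**Step 3: change between looks.** One variable's screen status changes somewhere across the three looks in about 37% of trials. For 5 independent candidates, the screened set changes with probability 1 − (1 − 0.372)⁵ ≈ 90%. After stepwise selection (odds ratio 2.0, model always fitted), the final set is identical at all three looks in 17–56% of trials, and in at least 83% of those it is empty.

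**Step 4: power.** Unadjusted SE = √(2 × 0.25 × 0.75 / 206) = 0.0427, so power = Φ(0.10/0.0427 − 1.96) = 64.9%. Simulated power with no true difference (%), model always fitted; ranges span the candidate counts and stepwise levels, and losses are taken within the same trials:

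| Odds ratio per SD | Unadjusted | Plan's rule | Fixed list | Loss, risk difference (points) | Loss, relative risk (points) |
|---|---|---|---|---|---|
| 1.5 | 64.4–65.6 | 64.4–66.0 | 64.9–66.8 | 0.5–0.9 | 0.4–0.9 |
| 2.0 | 63.3–65.7 | 64.7–66.2 | 67.2–68.5 | 1.7–2.5 | 1.7–2.8 |
| 2.7 | 64.0–65.6 | 66.1–67.3 | 70.0–71.2 | 3.4–4.4 | 3.4–4.7 |

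The relative-risk margin is 0.35/0.25 = 1.4. Check at odds ratio 2.0: mean SE 0.0423 (rule) gives Φ(0.404) = 65.7%, and 0.0411 (fixed list) gives Φ(0.473) = 68.2%, a gap of 2.5 points. With the illustrative trigger, risk-difference losses are 0.4–1.3 / 2.4–3.2 / 4.1–5.5. The second simulation, at joint R² 0.05 / 0.10 / 0.20 and one-sided 0.025, gave fixed list against rule 66.0 v 64.5, 69.0 v 65.7 and 73.6 v 67.9.

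**Step 5: error rate.** At true rates of 25% v 35%, one-sided type I error was 1.9–2.7% for the rule and 2.2–2.9% unadjusted (nominal 2.5%, Monte Carlo error 0.2). At odds ratio 2.0 the rule's reported SE of 0.0423 exceeds its true SD of 0.0411–0.0420, so it is slightly conservative. Picking the better of the two results afterwards adds 0.2–0.4 points in the first simulation and about 0.3 to 1 point in the second.

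**Step 6: disagreement.** With 5 candidates and entry at 0.15, unadjusted and rule-based non-inferiority verdicts differ in about 3 / 5 / 6% of trials at the three odds ratios. Unadjusted and fixed-list verdicts differ in about 5 / 8 / 12%.

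**The case against.** The strongest defence is that the model is offered as a check on confounding, not as a precision tool. Variables that fail the screen are those close to balance, so leaving them out does not bias the estimate, and the rule's power is about equal to or above that of the unadjusted analysis. The loss exists only against a list that contains a real predictor. This stands, and it limits the point to an efficiency gain not taken.

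Three stronger readings are tempting and not supported:

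- A reader might infer that selection by imbalance biases the result or inflates type I error. Step 5 shows no inflation from the rule; only a free choice of lead result adds error.
- A reader might take the disagreement between adjusted and unadjusted verdicts as evidence against the screen. A fixed list disagrees with the unadjusted result more often, so disagreement argues only for naming the lead result.
- A reader might assume two separate hurdles, a trigger and then the screen. The p < 0.25 rule may itself be the criterion for failed balance; the text does not settle this.

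It is also fair that the unadjusted results come unconditionally, which suggests they are the default, and that Section XII calls the trial exploratory. But the same document states non-inferiority and superiority hypotheses with formal looks, and one sentence would remove the doubt. No supplied text says that the adjusted model informs stopping, so the interim concern goes no further than an unnamed result.

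**Conclusion.** The point holds as a worthwhile, low-cost improvement, not as a validity flaw. The omission rate of about 75% or more follows from the screen alone and needs no assumption about prognostic strength. The size of the loss does: about 1 to 5 points of non-inferiority power over odds ratios of 1.5 to 2.7 per SD, and under 1 point at the low end if the model is always fitted. Candidate number, stepwise levels, margin and interval level are also assumed. Center clustering, group-sequential boundaries and the plan's own model types were not simulated. The criticism of the screen applies to intention-to-treat; in the per-protocol set, exclusions after randomization can create systematic imbalance. The statement that no lead result is named applies to the text available, without the CRF and the DSMB Charter.

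**What to change.** In Section XII, for the intention-to-treat analysis:

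1. Replace the imbalance trigger, the p < 0.25 screen and the stepwise step with a short fixed list of prognostic variables, measured before randomization and already on the CRF. Name the list before the first interim analysis or any unblinded look, use it unchanged at all three looks, and keep the allowance for center.
2. Name this adjusted analysis as the lead result, interim and final, and the unadjusted relative risk as supportive. State the effect scale; a log-link model keeps the relative risk already planned.
3. Give the per-protocol analysis its own pre-specified adjustment.

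Two covariates need care. Age is listed as protected health information in the data-handling text just before item XXVIa, which also keeps such information out of the analyst's file; clarify that age is supplied. Daily CPIS_clinical is a secondary outcome (Section IX), and randomization may come as late as the end of day four of therapy (Section X), so it qualifies only if a pre-randomization value is recorded.

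Cost: a minor amendment, which under Section XVIII needs approval from each local IRB. Sample size, looks and data collection need not change. Chance imbalance in an unlisted variable would be handled only in a sensitivity analysis, and the gain is small if the listed variables predict recurrence weakly.

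### Alpha of 0.05 is given no side, and 458 patients do not deliver the stated 80% power for recurrence non-inferiority at the level implied by the planned 95% interval

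*Combined protocol and SAP*

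**What the plan says.** Section XII gives one significance level for the whole trial: "The alpha error level is defined at 0.05, with statistical significance at $p < 0.05". Neither one-sided nor two-sided appears anywhere in the supplied text. For proportions the section names the chi-squared or Fisher test. On intervals it says: "Univariate analysis of categorical outcomes will be expressed as the relative risk with 95% confidence intervals". It gives no non-inferiority margin on that scale and no rule comparing a confidence limit with a margin. It also plans three analyses with an O'Brien-Fleming alpha spending function.

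Section VI has two kinds of hypothesis in view: "Assumptions for the power analysis include non-inferiority for VAP recurrence and superiority for antibiotic-free days in the intervention group". It takes 25% recurrence in the control group, three looks with binding futility boundaries, and six centers with an average cluster size of 10. It concludes: "To detect a 10% difference in outcomes between groups with 80% power and assuming a 10% dropout rate, a total sample size of 458 patients". It states no alpha, no recurrence rate for the 4-day arm and no intra-center correlation (ICC). The 10% is worded as a difference to detect and is never called a margin.

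**The concern.** A non-inferiority test looks in one direction only. An undirected 0.05 can therefore mean one-sided 5%, judged on a 90% interval, or one-sided 2.5%, judged on a 95% interval. The risk of accepting a 4-day course that is truly 10 points worse is 5% under the first reading and 2.5% under the second. The spending function also needs a total alpha and a side before either interim boundary can be computed, and so does the sample size recalculation that Section VI plans at each interim.

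The gap would be minor if the sample size pointed clearly to one level. It does not. At the one interval level the plan names, the stated power is not reached.

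**Working it through.** **Inputs.** From Section VI: control recurrence 25%, difference 10%, power 80%, dropout 10%, looks at 150, 300 and all patients. From Section XII: alpha 0.05. My assumptions: 25% recurrence in both arms for non-inferiority, 10% as an absolute margin in percentage points, 1:1 allocation, Lan-DeMets O'Brien-Fleming spending for alpha and for futility, and no clustering effect because no ICC is given. Evaluable patients: 458 × 0.9 = 412, or 206 per arm.

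**Step 1: try to reproduce 458.**

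Non-inferiority, n per arm = (z_alpha + z_power)² × [0.25 × 0.75 + 0.25 × 0.75] / 0.10².

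- One-sided 5%: (1.645 + 0.842)² × 0.375 / 0.01 = 231.8, so 232 per arm.
- One-sided 2.5%: (1.960 + 0.842)² × 0.375 / 0.01 = 294.3, so 295 per arm.

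Superiority, 25% vs 15%, n per arm = [z_alpha √(2 × 0.20 × 0.80) + z_power √(0.25 × 0.75 + 0.15 × 0.85)]² / 0.10².

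- One-sided 5%: 197 per arm.
- One-sided 2.5%: 250 per arm.

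Dropout divides the total by 0.9. The looks multiply it by 1.019 (efficacy only) to 1.069 (binding futility) at one-sided 5%, and by 1.012 to 1.059 at one-sided 2.5%.

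| Design | Fixed total | With dropout | With dropout and looks |
|---|---|---|---|
| Non-inferiority, one-sided 5% | 464 | 516 | 525 to 551 |
| Non-inferiority, one-sided 2.5% | 590 | 656 | 663 to 694 |
| 25% vs 15%, one-sided 5% | 394 | 438 | 446 to 468 |
| 25% vs 15%, one-sided 2.5% | 500 | 556 | 562 to 588 |

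Within 3% of 458 (444 to 472) there are only two matches, both at one-sided 5%. One is non-inferiority with the stated dropout and looks left out (464). The other is a superiority contrast of 25% vs 15% (446 to 468), which the protocol does not state for recurrence. The stated design with its stated dropout matches at neither level.

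**Step 2: power that 458 delivers for non-inferiority.** The standard error (SE) with 206 per arm is √(0.375 / 206) = 4.27 points, and 10 / 4.27 = 2.344.

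- One-sided 2.5%: Φ(2.344 − 1.960) = Φ(0.384) = 65% (64% with the efficacy looks).
- One-sided 5%: Φ(2.344 − 1.645) = Φ(0.699) = 76%.

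So about 11% of trials with truly equal arms would pass one rule and fail the other.

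**Step 3: does the level change the verdict?** Take 52/206 (7 days) vs 57/206 (4 days). The difference is 2.43 points and the unpooled SE is 4.34 points.

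- 90% upper limit: 2.43 + 1.645 × 4.34 = 9.6 points, non-inferior.
- 95% upper limit: 2.43 + 1.960 × 4.34 = 10.9 points, not shown.
- One-sided p against 10 points: z = (10 − 2.43) / 4.34 = 1.74, p = 0.041.

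The reversal remains at the final O'Brien-Fleming critical values (efficacy only): 2.43 + 1.69 × 4.34 = 9.8 points against 2.43 + 1.99 × 4.34 = 11.1 points.

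The largest observed difference that passes is 10 − 1.645 × 4.27 = 3.0 points at one-sided 5%, and 10 − 1.960 × 4.27 = 1.6 points at one-sided 2.5%.

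**Step 4: boundaries.** Critical values at 150, 300 and 458 patients (efficacy only) are 3.23, 2.16 and 1.69 at one-sided 5%, and 3.75, 2.54 and 1.99 at one-sided 2.5%.

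**The case against.** A reader might infer that 458 was computed at one-sided 5% while the analysis runs at one-sided 2.5%, so that design and analysis use alphas differing by a factor of two. The documents do not support this.

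- The match that includes dropout and looks needs a 15% rate that appears nowhere and a hypothesis not stated for recurrence. Other unstated inputs also reach 458. With a true benefit of 1.8 to 2.1 points in the 4-day arm, one-sided 2.5% reproduces it.
- Clustering is a listed input without an ICC. With an assumed ICC of 0.01 and the usual factor 1 + 9 × 0.01 = 1.09, every total rises. If patients are randomized within center and a factor of 1 − ICC is used, totals fall. Bringing 656 down to 458 would take a factor of 458 / 656 = 0.70, an ICC of about 0.30. That is large, but the documents do not exclude it.

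A reader might also say that Section XII prescribes two-sided tests. That is convention, not text. Only the 95% interval is explicit. It is on the relative risk, and the plan does not say that its limit decides non-inferiority. Read conventionally, alpha 0.05, p < 0.05 and 95% intervals agree with one another.

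Nor can it be shown that the analyst is free to choose the level after seeing the data. The DSMB charter is cited as an attachment, was not supplied, and may fix the boundaries.

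Three further objections have some force. The band of reversed verdicts is narrow. A properly written margin rule would have to name its confidence level anyway. The trial calls itself exploratory. However, that label is offered as the reason for not adjusting for multiplicity. It does not say which limit decides non-inferiority, and formal spending boundaries are planned regardless.

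What stands is that the side is missing, and that on the plain non-inferiority reading the stated power is reached at neither level.

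**Conclusion.** The point holds in this limited form. The level for the recurrence decision is undefined. At the level implied by the only interval the plan names, power is about 65% rather than 80%, and one-sided 5% raises it only to about 76%. The sample size cannot settle which level was meant.

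These figures rest on equal 25% recurrence, an absolute 10-point margin, equal allocation and no clustering effect. A stated ICC, a different margin scale or an assumed benefit of the shorter course would change them. The reversal band and the power comparison use fixed-sample critical values; the final O'Brien-Fleming values move the band slightly, to about 1.5 to 2.8 points. This should be corrected, because the choice can decide the trial's main conclusion.

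**What to change.** Amend Sections VI and XII before the next unblinded look:

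- **VAP recurrence:** judge non-inferiority at one-sided 0.025, using the upper limit of the two-sided 95% interval, with O'Brien-Fleming critical values run at that level for each look. If one-sided 0.05 was intended, say so, and make the deciding interval 90%.
- **Antibiotic-free days:** test superiority at two-sided 0.05.
- **Margin:** state it and its scale in the same place, so that the interval and the margin are comparable.
- **Section VI:** name the level, the 4-day arm rate and the ICC used, and restate the power that 458 delivers (about 65% or 76% on the assumptions here).

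The amendment needs a few sentences and no new data. The stated power becomes less favourable, and at one-sided 0.025 non-inferiority is harder to declare. Keeping 80% power would mean more patients: about 656 with dropout at one-sided 0.025, or 516 at one-sided 0.05, before looks and clustering. The sample size recalculation already planned at each interim is the natural place to take that decision.

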UM IRB No.: 20211211

NCT05545735

Protocol Date: November 14, 2023

Principal Investigator: [name]., M.S.P.H.

Study Title: The Duration of Antibiotic Therapy for Early VAP (DATE) Trial

Cover Page for Protocol

Sponsor name:	None
ClinicalTrials.gov ID#	NCT05545735
University of Miami IRB#	20211211
Brief title:	The Duration of Antibiotic Therapy for Early VAP (DATE) Trial
Official title of study:	The Duration of Antibiotic Therapy for Early VAP (DATE) Trial: A Surgical Infection Society Multicenter Randomized Clinical Trial of 4 vs. 7 Days of Definitive Antibiotic Therapy for Early Ventilator-Associated Pneumonia in the Surgical Intensive Care Unit
Document date:	November 14, 2023

UM IRB No.: 20211211

NCT05545735

Protocol Date: November 14, 2023

Principal Investigator: [name]., M.S.P.H.

Study Title: The Duration of Antibiotic Therapy for Early VAP (DATE) Trial

I. Protocol Title

The Duration of Antibiotic Therapy for Early VAP (DATE) Trial: A Surgical Infection Society Multicenter Randomized Clinical Trial of 4 vs. 7 Days of Definitive Antibiotic Therapy for Early Ventilator-Associated Pneumonia in the Surgical Intensive Care Unit

II. IRB Review History

Not applicable

III. Hypothesis and Specific Aims

The **hypothesis** of this randomized controlled trial (RCT) is that 4 days of antibiotic therapy, as compared to 7 days, is non-inferior regarding the primary outcome of ventilator-associated pneumonia (VAP) recurrence and superior in decreased antibiotic exposure among surgical intensive care unit (ICU) patients with early (within 2 – 7 days of intubation via endotracheal or tracheostomy tube) VAP. Our **specific aim** is to determine whether 4 days of antibiotic therapy is non-inferior to 7 days of antibiotic therapy for the treatment of early VAP with regards to recurrence and superior with regards to antibiotic exposure time.

IV. Background

The prevalence of multidrug resistant (MDR) pathogens in ICUs worldwide has reached epidemic proportions (1, 2). In some cases, the choice of potential therapy is limited or even nonexistent (3). Antibiotic prescription, through selection pressure, represents the main mechanism by which resistance emerges (4). Limitations in the development of new antibiotics (5) underscores the importance of adherence to the principles of antibiotic stewardship (6).

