- b.** Antibiotic-free days within 30 days

B) Secondary Outcomes

- a.** Antibiotic exposure
 - i.** Days of antibiotics
 - ii.** Antibiotic days (defined as the product of days of antibiotics and number of antibiotics per day)
- b.** Clinical improvement, measured using daily CPIS_{clinical} score while enrolled in the study
- c.** VAP relapse = recurrent VAP caused by initial pathogen (if culture data available), occurring 2 – 14 days following completion of initial therapy
- d.** 30-day Ventilator-free days

UM IRB No.: 20211211

NCT05545735

Protocol Date: November 14, 2023

Principal Investigator: [name]., M.S.P.H.

Study Title: The Duration of Antibiotic Therapy for Early VAP (DATE) Trial

- e. Empyema
- f. Need for tracheostomy
- g. Non-pulmonary infections
- h. 30-day ICU-free days
- i. Hospital LOS
- j. In-hospital Mortality

X. Procedures Involved

This is a multicenter, randomized, clinical trial. The trial will be reported in accordance with the recommendations of the CONSORT statement (18). IRB approval will be obtained. All subjects, or their legally authorized representatives, will provide written consent for study participation. The trial is registered with the US National Institutes of Health (ClinicalTrials.gov Identifier #NCT05545735).

Screening will occur daily by study personnel. Eligible patients will be approached as soon as possible after inclusion criteria are met (i.e., 1 – 3 days prior to randomization). Randomization will occur using a computer-generated block pattern no later than the end of the fourth day of appropriate antibiotic therapy. Randomization will occur at the hospital level in blocks of 20.

Empiric antibiotic therapy will be instituted as soon as possible following diagnosis of suspected pneumonia by the clinical team. The default antibiotic will be based on the local institutional antibiogram and practice. Pre-existing treatment for a non-pulmonary infection with at least one antibiotic that has appropriate activity against the VAP pathogen may be substituted for the default antibiotic. Once sensitivity data become available, therapy may be de-escalated to a more narrow-spectrum agent, as indicated.

The default duration of antibiotic therapy will be determined by study group assignment; the treatment team will be asked to adhere to study group assignment whenever possible. However, the treatment team may choose to extend the duration of antibiotic therapy based on

UM IRB No.: 20211211

NCT05545735

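### Section XII calls a powered, two-primary non-inferiority trial exploratory and gives no joint success rule, so a result on antibiotic-free days alone could be presented as a primary success

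*Combined protocol and SAP*

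**What the plan says.** Section IX (Study Endpoints) lists two primary outcomes, "VAP recurrence within 30 days" and "Antibiotic-free days within 30 days".

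Section III (Hypothesis and Specific Aims) states one hypothesis with two parts: the 4-day course "is non-inferior regarding the primary outcome of ventilator-associated pneumonia (VAP) recurrence and superior in decreased antibiotic exposure". The specific aim repeats the pairing, ending "with regards to recurrence and superior with regards to antibiotic exposure time". Section VI (Number of Subjects) assumes "non-inferiority for VAP recurrence and superiority for antibiotic-free days in the intervention group", with 80% power, three analyses, an O'Brien-Fleming spending function and binding futility boundaries.

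Section XII (Data Management) sets alpha at 0.05, applies O'Brien-Fleming spending to all outcomes at the three looks, and then says: "No adjustment for multiplicity of outcomes will be done as this is an exploratory (rather than confirmatory) trial". It adds that all hypotheses are pre-planned and that adjusting for multiple comparisons raises type II error. Section XIII lets the DSMB end the study for clear benefit in either group without naming the outcome on which benefit is judged.

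**The concern.** Sections III and VI describe a confirmatory trial: a directional joint hypothesis, a power target and formal boundaries. Section XII describes an exploratory one and uses that label to justify having no rule across the two primaries. Both descriptions cannot govern the same result, and a non-inferiority conclusion about treatment duration is weakened if the plan itself disclaims a confirmatory purpose.

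The two primaries are also unlike each other. Recurrence is the outcome on which the shorter course could do harm. Antibiotic-free days is largely a consequence of assignment, since one arm is asked to stop three days sooner. Without a rule tying them together, the second can be significant while the first fails, and nothing in Section XII says that this is not a positive trial. The same gap applies at the interim looks, because all outcomes are analysed there and clear benefit is not tied to recurrence.

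**Working it through.** **Plan figures.** The plan states no familywise error rate, and no SD, expected difference or power for antibiotic-free days, so there is no figure of its own to reproduce on this point. The one plan number used is N = 458 with 10% dropout (Section VI): 458 × 0.9 / 2 = 206 evaluable per arm. That total did not reproduce from all the stated inputs. For non-inferiority with 25% in both arms, a 10-point margin and 80% power, n per arm = 2 × 0.25 × 0.75 × (z_α + z_β)² / 0.10². This gives 232 per arm (464 in total) at one-sided 0.05 and 295 (590) at one-sided 0.025, before dropout. Sidedness and the intraclass correlation are not given, so I take 458 as stated; the point does not depend on it.

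**Step 1: the net difference in antibiotic-free days if 4 days is truly worse.** Suppose recurrence is 10 points higher on 4 days and each extra recurrence is treated for 7 days (assumption). The cost is 0.10 × 7 = 0.7 day.
- Full 3-day gap: 3 − 0.7 = 2.3 days.
- Gap diluted by about 30% (assumption, for the extensions that Section X allows): 0.7 × 3 − 0.7 = 1.4 days.

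**Step 2: chance that antibiotic-free days is significant.** Power = Φ(d / (SD × √(2/206)) − 1.96), two-sided 0.05, normal approximation, no clustering. The SDs are assumed.

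| SD (days) | Standard error | d = 1.4 | d = 2.3 |
|---|---|---|---|
| 6 | 0.591 | 0.658 | 0.973 |
| 8 | 0.788 | 0.427 | 0.831 |
| 10 | 0.985 | 0.295 | 0.646 |

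This is about 43–83% at SD 8 and roughly 30–97% over the whole range.

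**Step 3: allow for recurrence.** Take the 10% in Section VI as the margin; the plan calls it a difference to detect. With a true 10-point excess, non-inferiority is then shown with probability about 0.025 to 0.05, the one-sided level. The chance that antibiotic-free days is significant and non-inferiority is not shown therefore lies within 5 percentage points of each figure in the table, whatever the correlation between the outcomes.

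**Step 4: would an alpha split cure it?** Put 2.241 (two-sided 0.025) in place of 1.96. At SD 8, Φ(1.776 − 2.241) = 0.32 and Φ(2.918 − 2.241) = 0.75, against 0.43 and 0.83. A split lowers the chance a little and leaves the problem. What is missing is the joint rule, not an adjustment.

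**Step 5: error under a joint rule.** If both must succeed, a false claim requires passing a test whose null is true, so the error is at most the level of a single test (0.05 as the plan sets it). No split is needed. The type II error argument in Section XII concerns splitting alpha and does not apply to this rule.

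**Step 6: interim look at 300 patients.** With 150 per arm, an O'Brien-Fleming-type bound of about 2.51 and the same net gains, power = Φ(d / (SD × √(2/150)) − 2.51). At SD 8 the standard error is 0.924, giving Φ(1.516 − 2.51) = 0.16 and Φ(2.490 − 2.51) = 0.49. Antibiotic-free days alone could cross an efficacy bound in a trial where the short course is worse on recurrence.

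**The case against.** The strongest reply is that the plan already implies the right rule. The hypothesis, the specific aim and the power assumptions all join the two outcomes with *and*, and the hypothesis calls only recurrence the primary outcome. On that reading a win on antibiotic-free days alone fails the stated hypothesis, no adjustment is needed, and the waiver does little harm. This stands in part. An either-one success rule is nowhere stated; it is only left open. But Section IX lists both outcomes as primary, and Section XII, where the decision rule belongs, replaces the conjunction with an exploratory label.

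It is also fair to say that a real difference in antibiotic-free days is a true finding and not a type I error. That is accepted, and it is why the remedy is a joint rule and not an alpha penalty.

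Three stronger readings are tempting and are not supported:
- A reader might infer that a win on antibiotic-free days is practically assured. The plan gives no SD, and Section X lets teams extend therapy for deterioration, procalcitonin results or non-pulmonary infection. At a 1.5-day gap and SD 8, power is about 48%.
- A reader might infer an inflated familywise error by combining the two 5% tests, or many secondary outcomes. For the primaries that needs an either-one rule and a true null on antibiotic-free days, which assignment makes unlikely. The secondaries are correlated, and two of them measure antibiotic exposure directly.
- A reader might infer that multiplicity is uncontrolled altogether. Repeated looks are controlled by O'Brien-Fleming spending; only multiplicity across outcomes is waived.

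**Conclusion.** The concern holds as a contradiction together with a missing decision rule. The exploratory label in Section XII cannot be squared with the joint hypothesis in Section III or the powered, alpha-spending design in Section VI, and nothing in the text provided prevents antibiotic-free days alone from being presented, or acted on at an interim look, as a primary success.

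The size is uncertain. The 30–97% range rests on the assumed SD, dilution and re-treatment length; only the 206 per arm comes from the plan. Even its lower end is too high to leave the matter to interpretation. The DSMB charter is mentioned as an attachment but is not among the documents, so it may already define the stopping outcome. This should be corrected before the final analysis, and before any interim look that remains.

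**What to change.** In Section XII, delete the sentence that justifies the approach by calling the trial exploratory. In its place state that:
- the trial succeeds only if non-inferiority on recurrence and superiority on antibiotic-free days are both shown, each tested at the full overall alpha under the existing spending function, with no split;
- antibiotic-free days alone supports neither a positive trial conclusion nor a statistical efficacy stop at an interim analysis, and Section XIII and the DSMB charter should agree with this;
- secondary outcomes remain unadjusted and are described as supportive.

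The DSMB's ability to stop for safety is unaffected. The cost is one paragraph, with no alpha and no added patients. The downside is that no positive trial claim can be made from antibiotic-free days alone; that result would still be reported with its estimate and interval.
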